7.4.2. Randomization

Randomization is to occur only after verification of all inclusion/exclusion criteria. Once the subject has signed the Institutional Review Board (IRB)/Ethics Committee (EC)-approved study ICF and has met all general inclusion and none of the exclusion criteria, the subject will be eligible for randomization. Randomization schedules will be computer-generated in advance, using a pseudo-random number generator and loaded into the EDC system. Randomization assignments will be obtained from the EDC system at the time of procedure. Randomization will be stratified by clinical site. Within each site, eligible subjects will be randomized in a 1:1 ratio to receive each treatment method.

For back-up randomization, sites will be instructed to randomize subjects via back-up envelopes only in cases of unsuccessful EDC access. Envelopes are sequentially numbered sealed opaque envelopes containing randomized treatments.

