8.6.2. Post-Procedure Endpoints

Post-procedure information will be collected at regularly scheduled follow-up examinations as detailed in the clinical trial schedule and will be summarized using descriptive statistics for continuous variables and frequency statistics for discrete variables. Estimates of primary and secondary endpoints will be reported by treatment group, as well as differences between treatment groups and their 95% confidence intervals.

Impact of baseline variables on endpoints will be analyzed using logistic regression, ANOVA, stratified methods or Kaplan-Meier methods per section 8.6.1 and the SAP.

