3.1.2 Sample Size

A literature search of metal and or plastic stenting for treatment of benign biliary strictures secondary to chronic pancreatitis yielded 4 articles representing 70 subjects treated with metal stenting (MS)²⁻⁷ and 3 articles representing 60 subjects treated with plastic stenting (PS)⁸⁻¹³.

The following meta-analysis was conducted of the probability of stricture resolution:

- Metal Stenting: A meta-analysis of the stricture resolution rate during the reported follow-up after initial stent placement yields a proportion of 0.762 [95% CI: 0.593 0.895]²⁻⁷.
- Plastic Stenting: A meta-analysis of the stricture resolution rate during the reported follow-up after initial stent placement yields a proportion of 0.611 [95% CI: 0.311 0.870] ⁸⁻¹³.

The sample size was calculated for a one-sided 0.050 Farrington-Manning test using SAS 9.2®. If the P value from the Farrington-Manning test is <0.05 then the metal stent group will be considered non-inferior to the plastic stent group. The expected probability of a stricture resolution in the metal stent arm and plastic stent arm is 66.0%, which was taken from the 95% CIs from the meta-analysis above. The non-inferiority margin (Δ) is 20%. Given these assumptions, and a one-sided 5% significance level, 2 x 74 = 148 subjects will provide 80% power to reject the null hypothesis, that the metal stent group is inferior to the plastic stent group. To compensate for possible loss of subjects between enrollment and complete assessment of inclusion/exclusion criteria and subsequent randomization, an additional 10% of subjects will be enrolled for a total of 2 x 82 = 164.

Version AA March 20, 2013 Boston Scientific WallFlex Biliary FC CP RCT SAP 90913894/Ver. AA Page 8 of 13

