3.1.3 Statistical Methods

Eligibility of Subjects, Exclusions, and Missing Data

The distribution of prognostic factors between patients with and without data will be examined. Statistical models that account for censored data will be employed in appropriate circumstances, e.g. for time-to-event outcomes.

For calculating the rate of stricture resolution at 24 months after initial stent placement, patients with insufficient follow-up will be excluded from the calculation; that is, only patients that have at least follow-up through 24 month visit will be included. Sensitivity analyses, such as a tipping point analysis will be performed to assess the impact of the missing data, if the data support such analysis.

When calculating rates of adverse events, missing and partial dates will be handled as follows:

Partial Date Description	Action Taken	
Entire onset date is missing	The procedure date will be used for the	
	onset date.	
The month and the day of the month are	January 1 will be used for the month and	
missing but the year is available	day of the onset date. However, if the	
	imputed date falls before the procedure	
	date, then the procedure date will be used	
	for the onset date.	
Day is missing, but the month and year are	The 1 st will be used as the day of the onset	
available	date. However, if the imputed date falls	
	before the procedure date, then the	
	procedure date will be used for the onset	
	date.	

Baseline Comparability

Baseline data will be analyzed to assess the comparability of the treatment groups. Patient demographics, clinical history, risk factors, and procedure characteristics will be summarized using descriptive statistics (mean, standard deviation, n, minimum, maximum) for continuous variables and frequency statistics for discrete variables. Statistical testing will be performed using appropriate methods.

Post-Procedure Endpoints

The treatment effect due to important prognostic factors at the baseline level for both groups will be assessed using the logistic regression model for categorical outcomes, analysis of covariance model for continuous outcomes, or stratified methods, as appropriate.

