Version AA March 20, 2013 Boston Scientific WallFlex Biliary FC CP RCT SAP 90913894/Ver. AA Page 9 of 13 Overall safety and effectiveness will be reported based on patients with sufficient followup by Metal Stent Arm and Plastic Stent Arm using the logistic regression or analysis of covariance model adjusted for baseline covariates. The Kaplan-Meier product-limit method will also be used to estimate event-free rates for time-to-event outcomes and compared using log-rank and Wilcoxon tests. Additional analyses will be performed as appropriate.

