5.4 Justification of Pooling

The analyses will be presented using pooled data across institutions. An analysis of the poolability will be made using logistic regression for binary outcomes, proportional hazards regression for time-to-event outcomes, or analysis of variance for continuous outcomes, to assess differences between study institutions and to justify pooling data across institutions.

Version AA March 20, 2013 Boston Scientific WallFlex Biliary FC CP RCT SAP 90913894/Ver. AA Page 11 of 13

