7.3 Rules and Definitions

Binary event rates (proportions) will be reported on a per patient basis.

The last follow-up date will be the latest of the following dates for each patient: date of an adverse event, index procedure date, follow-up visit date, any stent or ECRP procedure date, stent removal date, and device event date.

Stricture resolution at 24 months is defined by the following two criteria being met:

• Absence of re-stenting after the per-protocol stenting period through the 24 month visit

Version AA March 20, 2013 Boston Scientific WallFlex Biliary FC CP RCT SAP 90913894/Ver. AA Page 12 of 13 • Absence of cholestasis at the 24 month visit, defined as alkaline phosphatase level not exceeding 2 times the level at completion of the per-protocol stenting period

Primary endpoint failures are 1) subjects who are re-stented during follow-up after the per-protocol stenting period and 2) subjects who have not been re-stented at month 24 but have alkaline phosphatase level exceeding 2 times the level at completion of the per-protocol stenting period.

Subjects who experience early stent removal or complete distal stent migration without subsequent re-stenting will not be considered failures. If re-stenting occurs, but the cumulative stenting period does not exceed 12 months, the subject remains eligible for primary endpoint assessment.

For the final tables, two-sided exact tests will be done to test for differences between the two groups for removability and AEs. A one-sided non-inferiority Farrington-Manning test will be done to see if stricture resolution is non-inferior in the Metal group compared to the Plastic group. A two-sided student's t-test will done to test for differences between the two groups for the number of ERCP procedures done.

Version AA March 20, 2013 Boston Scientific WallFlex Biliary FC CP RCT SAP 90913894/Ver. AA Page 13 of 13

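### Minor: randomization is stratified by clinical site, but the primary non-inferiority test and the reported confidence interval leave site out

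*SAP*

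**What the plan says.** Protocol 7.4.2: "Randomization will be stratified by clinical site", with equal allocation inside each site. Schedules are generated by computer in advance; blocking is not mentioned. The synopsis allows up to 15 sites.

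SAP 3.1.2: "The sample size was calculated for a one-sided 0.050 Farrington-Manning test", with 66% resolution expected in both arms, a 20-point margin and 74 evaluable subjects per arm. SAP 7.3 repeats the choice: "A one-sided non-inferiority Farrington-Manning test will be done to see if stricture resolution is non-inferior in the Metal group". Neither section names strata or a site term.

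Protocol 8.6.2 promises estimates by group and "differences between treatment groups and their 95% confidence intervals", again without stratification.

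Site does appear elsewhere:
- Protocol 8.6.1 compares baseline characteristics among centers, and Protocol 8.6.2 links its covariate analyses to that section.
- SAP 5.4 says "The analyses will be presented using pooled data across institutions" and adds a regression check of differences between institutions; Protocol 8.6.3 points to the same check.
- SAP 3.1.3 allows logistic or covariance models "or stratified methods, as appropriate" for prognostic factors, and reports effectiveness "using the logistic regression or analysis of covariance model adjusted for baseline covariates". Site is not named in either place.

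None of these changes the primary test.

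**The concern.** When randomization forces the arms to balance within site, differences between sites cancel out of the treatment comparison. An analysis that ignores site still counts that variation as noise, so its standard error is too large. The test then rejects less often than its nominal 5%, and the interval is wider than it need be. What is at stake is a little power and precision. The error is on the cautious side for a non-inferiority claim.

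**Working it through.** **Inputs from the documents.** One-sided alpha 0.05; 66% in both arms; margin 0.20; 74 evaluable per arm, 82 randomized per arm; up to 15 sites; 1:1 within site. **Not in the documents, so assumed over a range:** whether allocation is blocked, and how far site resolution rates differ.

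**1. The plan's own figure.** The Farrington-Manning formula uses restricted null rates of 0.547 and 0.747:

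n = [1.645 × √(0.547×0.453 + 0.747×0.253) + 0.842 × √(2×0.66×0.34)]² / 0.20² = 68.2, so 69 per arm.

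The stated 74 is not reproduced with the named test. An unpooled variance at 66% and 46% does give it: (0.2244 + 0.2484) × (1.645 + 0.842)² / 0.04 = 73.1, so 74. At 74 per arm the Farrington-Manning power is 82.8% (approximate) or 83.2% (exact). This mismatch is on the safe side and does not affect the present point.

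**2. Direction, in large samples.** At the null (66% against 46%) the pooled analysis uses a variance proportional to 0.66×0.34 + 0.46×0.54 = 0.4728. With perfect balance within site and a between-site SD s on the probability scale, the true value is 0.4728 − 2s². With r = √[(0.4728 − 2s²)/0.4728], the one-sided size is 1 − Φ(1.645/r).

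| s | r | size | coverage of 95% CI |
|---|---|---|---|
| 0.05 | 0.995 | 4.9% | 95.1% |
| 0.10 | 0.979 | 4.6% | 95.5% |
| 0.15 | 0.951 | 4.2% | 96.1% |
| 0.20 | 0.911 | 3.6% | 96.8% |

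Without balance within site, chance imbalance brings the site variation back into the comparison. The pooled standard error is then not too large: simulated size under simple randomization is 5.0 to 5.4%.

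**3. Size at this trial's scale.** Simulation assumptions: 164 randomized, 15 unequal sites, 10% random loss, normal site effects on the logit scale. Sites with fewer than 2 evaluable subjects in either arm are combined (about 3 of 15 sites if blocked, 4 if not). Two runs of 60,000 replicates were averaged (error about 0.06 points for size, 0.1 for power); interval widths come from one run. Stratified means a Mantel-Haenszel difference with score variance.

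| Logit SD | Site rates at −1/+1 SD | Blocked: size, pooled / stratified | Blocked: power, pooled / stratified | Unblocked: power, pooled / stratified |
|---|---|---|---|---|
| 0 | 66 / 66% | 5.3 / 5.2% | 82.8 / 82.1% | 82.6 / 80.5% |
| 0.5 | 55 / 77% | 4.9 / 5.1% | 83.5 / 83.5% | 82.7 / 81.7% |
| 0.65 | 52 / 80% | 4.6 / 5.0% | 83.9 / 84.4% | 82.9 / 82.8% |
| 0.8 | 49 / 83% | 4.5 / 5.2% | 84.3 / 85.3% | 82.7 / 83.4% |
| 1.0 | 45 / 86% | 4.3 / 5.2% | 84.9 / 86.7% | 83.1 / 84.7% |

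Blocked means blocks of 4; blocks of 6 gave nearly the same power.

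- Blocked, power gain from stratifying: −0.7, 0.0, +0.5, +1.0, +1.8 points down the table.
- Unblocked: −2.1, −1.0, −0.1, +0.7, +1.6 points. Size is 5.1 to 5.5% for both tests.
- Half-width of the 95% CI, blocked: pooled 15.2 points at SD 0 and 15.1 at every other SD; stratified 15.3, 14.9, 14.7, 14.4, 14.0.

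**4. Cross-check.** A simpler simulation used 15 equal sites, near-perfect balance, 74 per arm and Sato variance. At probability SD 0 / 0.05 / 0.10 / 0.15 / 0.20, power was 83.2 / 83.2 / 83.7 / 84.2 / 85.3% pooled and 82.5 / 82.7 / 83.9 / 85.5 / 88.2% stratified. The gain is again about nil up to 0.10. It reaches about 3 points at 0.20 under these ideal conditions.

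**The case against.** The case for leaving the plan alone is strong, and much of it stands.

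- **Pooling is a declared choice.** The documents say that data will be pooled, check that choice, and compare centers at baseline. That is correct, but none of it brings the randomization stratum into the primary test.
- **The gain may be nil.** At logit SD 0.5, where sites already run from 55% to 77%, power is the same under both tests. Discreteness is as large as the site effect: with no site differences the exact size of the Farrington-Manning test is 5.7% at 74 per arm and 4.7 to 4.8% at 71 to 73. So *conservative* means relative to the same test without site differences.
- **Stratifying can cost as much as it gains.** If allocation is unblocked and sites differ little, it loses 1 to 2.6 points (the larger figure with Sato variance, down to 80.0% power). With 148 evaluable subjects in 15 sites, strata average about 5 per arm, so a combining rule is unavoidable. This is why the remedy depends on blocking.

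Three stronger readings are tempting but not supported:

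- A reader might infer that two competing tests leave room to choose after the data are seen. SAP 3.1.2 gives a single decision rule on the Farrington-Manning P value, and SAP 7.3 names the same test. No section lets a stratified result replace it.
- A reader might take the wide meta-analysis intervals in Protocol 8.2 as evidence that sites will differ greatly. Those intervals combine 3 or 4 articles. Protocol 1.2 itself reports success of 24 to 46% with single and 62 to 92% with multiple plastic stents. Variation of that kind is not variation between sites under one protocol.
- A reader might infer that the non-inferiority conclusion is unsafe. The calculations point the other way.

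**Conclusion.** The point holds as a minor, inexpensive improvement. Site is a randomization stratum, and neither the primary test nor the reported difference with its interval uses it. If allocation is balanced within site and the logit SD between sites is about 0.65 or more, this makes the pooled analysis slightly conservative: size falls to about 4.6 to 4.3%, about 0.5 to 2 points of power are forgone, and the interval half-width is about 0.4 to 1.1 points larger than it need be. Most of that power gain is unused alpha rather than extra efficiency. With smaller site differences nothing is gained.

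Ignoring site does not produce a false non-inferiority claim, and pooled power is 82.6 to 84.9% across the main simulations. The sizes rest on assumed site variation, site sizes and random loss. Blocking and the true spread between sites cannot be read from the documents.

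**What to change.** In SAP 3.1 and 7.3, prespecify a site-stratified Mantel-Haenszel risk difference (metal minus plastic), with stratified score or Sato variance, tested one-sided at 5% against the 20-point margin. Take the 95% interval promised in Protocol 8.6.2 from the same method. Add a rule for combining small sites, fixed before outcomes by arm are seen; for example, sites with fewer than 2 evaluable subjects in either arm form one stratum.

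- **If the schedule is blocked within site:** make the stratified analysis primary and report the pooled Farrington-Manning test as supportive.
- **If it is not blocked:** keep the pooled test primary and report the stratified analysis as a sensitivity analysis.

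The cost is SAP wording and minor programming, with no change to sample size or conduct. If sites turn out not to differ, a stratified primary test loses about 1 point of power under blocking (0.7 with score variance, 1.1 with Sato). Without blocking it would lose 2 to 3 points (2.1 and 2.6), which is why it should not be primary there. Under blocks of 4 its size is 5.0 to 5.4%, slightly above nominal at the largest site SD.

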Complications inclusive of all subjects in all studies of metal stents included migration (5%-16.2%)^{1,9,11}, bleeding (1%-5%)^{1,9,10}, pain (2%-5%)^{1,9,10}, pancreatitis (5%-13.9%)^{1,9,11}, cholangitis (4.6%-35%)¹¹ and occlusion (9.3%)¹¹.

2. Device Description

The WallFlex Biliary RX Fully Covered Stent System RMV is indicated for use in the palliative treatment of biliary strictures produced by malignant neoplasms, and for treatment of benign biliary strictures, per CE Mark. This clinical study will be conducted only in countries where this indication for use is cleared or approved per local regulatory requirements. Enrolled subjects will have benign biliary strictures secondary to chronic pancreatitis.

Study devices are labeled on the box and inner pouch and include information not limited to name of legal manufacturer, device name and dimensions, lot number, expiration date and investigational use statement. Device labeling will be provided in local language(s) as per national regulations.

For a detailed description of the WallFlex Biliary RX Fully Covered Stent System RMV, please reference the Directions for Use (DFU) included in each device package.

The DFU indicates stent placement for the following use: the palliative treatment of biliary strictures produced by malignant neoplasms, and for treatment of benign biliary strictures. Investigators should use the WallFlex Biliary RX Fully Covered Stent System RMV in accordance with the DFU.

Description	Delivery System Working Length (cm)	Stent Diameter (mm)	Stent Length (mm)
WallFlex Biliary RX Fully Covered Stent System RMV	194	8	60
WallFlex Biliary RX Fully Covered Stent System RMV	194	8	80
WallFlex Biliary RX Fully Covered Stent System RMV	194	10	40
WallFlex Biliary RX Fully Covered Stent System RMV	194	10	60
WallFlex Biliary RX Fully Covered Stent System RMV	194	10	80

3. Primary Objectives

To compare the use of Self Expanding Metal Stents (SEMS) to plastic stents for the treatment of benign biliary strictures secondary to chronic pancreatitis as it pertains to stricture resolution rates, complication rates and number of ERCP procedures during 24 months.

4. Endpoints

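### Stricture resolution has a planned non-inferiority test and a planned 95% interval but no superiority hypothesis or decision rule; a fixed-sequence step could be added without alpha cost

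*SAP*

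**What the plan says.** The primary objective (Protocol section 3, repeated in SAP section 1) is general: "To compare the use of Self Expanding Metal Stents (SEMS) to plastic stents" on resolution, complications and number of ERCPs. Protocol 8.1 and 8.2 narrow the statistical aim for resolution to non-inferiority.

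The design is in SAP 3.1.2: "The sample size was calculated for a one-sided 0.050 Farrington-Manning test using SAS 9.2"; "The non-inferiority margin (Δ) is 20" percentage points; "The expected probability of a stricture resolution in the metal stent arm and plastic stent arm is 66.0" per cent; "2 x 74 = 148 subjects will provide 80% power to reject the null hypothesis"; and "an additional 10% of subjects will be enrolled for a total of 2 x 82 = 164". The same section gives pooled literature rates. For metal the analysis "yields a proportion of 0.762" (95% CI 0.593 to 0.895; 70 subjects in 4 articles). For plastic it gives 0.611 (0.311 to 0.870; 60 subjects in 3 articles).

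SAP 7.3 names the test for each outcome. Removability and adverse events get two-sided exact tests of difference, and ERCP count gets a two-sided t-test. For resolution, "A one-sided non-inferiority Farrington-Manning test will be done to see if stricture resolution is non-inferior in the Metal group".

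Two other places bear on resolution by arm. Protocol 8.6.2 plans between-arm differences with 95% intervals for primary and secondary endpoints. SAP 3.1.3 plans covariate-adjusted models of effectiveness by arm. Neither states a superiority hypothesis or criterion.

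**The concern.** The objective is a general comparison, and removability, adverse events and ERCP count each have a planned test of difference. Resolution, the primary endpoint, does not. If metal is really better, the planned test will very probably succeed, but it will establish only that metal is not more than 20 points worse.

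The planned 95% interval will be reported in any case, and readers will look at whether it excludes zero. Without a rule written beforehand, nothing fixes whether that counts as a formal finding, at what level, or in which subjects. What is at stake is how much the trial can formally conclude from the same data. The validity of the planned conclusion is not in question.

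**Working it through.** **Inputs (SAP 3.1.2).** One-sided alpha 0.05, margin 0.20, planning rate 0.66 in both arms, 74 evaluable and 82 enrolled per arm, literature rates 0.762 and 0.611.

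**1. The plan's own sample size.** With unpooled variance, n = (1.645 + 0.842)² × 2 × 0.66 × 0.34 / 0.20² = 69.4, so 70 per arm. With the Farrington-Manning restricted null rates (0.547 and 0.747), n = [1.645 × √(0.547 × 0.453 + 0.747 × 0.253) + 0.842 × √(2 × 0.66 × 0.34)]² / 0.20² = 68.2, so 69. The stated 74 is not reproduced exactly but is slightly generous: exact power of the Farrington-Manning test at 66% in both arms is 83.2% with 74 per arm and 86.0% with 82. The step to 82 is 74 × 1.1 = 81.4, rounded up. None of this affects the point.

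**2. Non-inferiority test at the literature rates.** Exact enumeration gives power of 99.87% (74 per arm) and 99.94% (82 per arm).

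**3. Superiority step at the literature rates.** The difference is 0.762 − 0.611 = 0.151 and the mean rate is 0.6865.
- Null SE = √(2 × 0.6865 × 0.3135 / n), which is 0.0763 at n = 74 and 0.0725 at n = 82.
- The observed difference needed at two-sided 5% is 1.96 × SE, which is 0.149 and 0.142.
- Alternative SE = √[(0.762 × 0.238 + 0.611 × 0.389) / n], which is 0.0753 and 0.0715.
- Power = Φ[(0.151 − needed difference) / alternative SE], which is 50.8% and 55.0%. Exact enumeration gives 51.4% and 55.4%.
- For 80% power, n = [1.96 × √(2 × 0.6865 × 0.3135) + 0.842 × √(0.762 × 0.238 + 0.611 × 0.389)]² / 0.151² = 147 per arm.

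**4. Alpha.** All possible outcome tables at 74 and at 82 per arm were enumerated, with the Farrington-Manning test at one-sided 5% followed by the zero-difference score test at two-sided 5%.
- No table rejects for superiority without also rejecting for non-inferiority.
- With 66% in both arms, false superiority of metal occurs in 2.5% of trials.
- At the margin (46% vs 66%) it occurs in less than 0.01%.
- The non-inferiority test is unchanged.

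**5. The interval already planned.** If exactly 76.2% and 61.1% were observed, the Wald 95% interval would be 0.151 ± 1.96 × 0.0753, or 0.4 to 29.8 points (74 per arm). With 82 per arm it would be 1.1 to 29.1. Either just excludes zero.

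**6. Direction of the hypotheses.** SAP 3.1.1 defines π as the probability of resolution but prints H0: π_test − π_control ≥ Δ. With Δ = 0.20, rejecting that null would show only that metal is less than 20 points better. A clearly better metal arm could then fail the first step, so the sequence cannot be built on the hypotheses as printed.

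**The case against.** The strongest reply is that this is a design preference. Protocol 8.1 and 8.2 state non-inferiority as the aim and SAP 7.3 carries it out. The word compare in the objective covers three outcomes, each of which has a planned test. This stands, and it is why the point is not an error.

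A reader might infer that any advantage for metal could be claimed only post hoc. The documents do not support that. The difference and its 95% interval are pre-specified in Protocol 8.6.2, and an adjusted model by arm in SAP 3.1.3. What is missing is the hypothesis and the rule, not the estimate.

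A reader might also infer that the plan expects metal to be better. It does not: it assumes 66% in both arms. The literature rates come from separate small series with overlapping intervals of about 59 to 90% and 31 to 87%. The near-certain non-inferiority result in step 2 belongs to that scenario alone; under the design assumption, power is 83 to 86%.

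Finally, the step would be underpowered, and a bare reference to the ITT cohort would not settle who is analysed. SAP 4.1 does not say which cohort is primary, and SAP 3.1.3 drops patients without 24-month follow-up. Both objections stand and are met in the fix. Low power is no reason to omit the step, since failing it leaves the non-inferiority result intact.

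**Conclusion.** The point holds as an optional improvement. Resolution has one hypothesis test with a decision rule, and no superiority hypothesis, order or rule, so a claim that metal is better would rest on an estimated interval without formal pre-specified status. A fixed-sequence step removes that gap without alpha cost.

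The gain is moderate: about a 51% (74 per arm) to 55% (82 per arm) chance of formally showing superiority, if the true rates are 76.2% and 61.1%. The chance is lower if the true advantage is smaller. The 74 figure is the more relevant one, because the plan is powered on it and patients without 24-month follow-up are excluded from the rate. No planned conclusion is invalidated by leaving the step out.

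**What to change.** First correct SAP 3.1.1, and the matching text in SAP section 1, the Protocol synopsis and Protocol 8.1, to H0: π_test − π_control ≤ −0.20 against Ha: π_test − π_control > −0.20. The sentence describing the null as non-inferior needs the same correction.

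Then add to SAP 7.3:

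> If non-inferiority is shown, superiority of metal will be tested with the zero-difference score test at two-sided 5% (consistent with the planned 95% CI), on all randomised subjects, with the tipping-point analysis of SAP 3.1.3 applied to subjects without a 24-month outcome. The fixed sequence needs no alpha adjustment.

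SAP 3.1.3 makes the tipping-point analysis conditional on the data supporting it. For this step it should be unconditional, and the starting assumption for missing outcomes should be named.

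Also state that power for this step is only about 51% (74 evaluable per arm) to 55% (82 per arm) even at 76.2% vs 61.1%, so that failing to show superiority would be uninformative and would not affect the non-inferiority conclusion.

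The cost is a few sentences of text, with no added patients, visits or data. The changes should be approved before comparative data are seen, including the informal interim summary after the first 50 subjects.
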